1.2.1 Dose Fractionations in SBRT

Similar to 3DCRT, adequate biologic equivalent dose (BED) is essential for optimal tumor control with SBRT [129, 130, 140, 143, 151-154]. SBRT normally delivers much higher BED than conventionally fractionated 3DCRT (typically BED of 70-85 Gy). Studies from Japan, Germany, and China all reported that SBRT with $BED \geq 100$ Gy was associated with significantly better local control and long-term survival. For patients who received a $BED \geq 100$ Gy, local tumor control was over 90%. The largest series [129] retrospectively reviewed 257 patients treated at 14 institutions in Japan using a number of different treatment doses and delivery approaches. At a median follow up of 38 months, the local recurrence rate was 8.4% in patients who were treated to a $BED \geq 100$ Gy. A recent Germany study also reported that a $BED > 100$ Gy is critical for achieving good local control [143]. A Chinese study applied daily fractionated SBRT with a total BED up to 115 Gy and reported 3- and 5-year OS rates for T1-3 patients of 57.3% and 35.1%, respectively, and for stage T1-2 patients of 60.2 and 36.5%, respectively [151]. Studies from the U.S. also suggested that patients who received 16 Gy x 3 (BED=124 Gy) had significantly better local control than those who received lower doses. Dose response analysis showed that the outcome plateaued around 120 Gy BED.

The effect of fractionation is complicated for SBRT, and fractionation regimens vary from center to center. A number of fractionation schedules are undergoing evaluation [155]. In the U.S., a frequently used schedule for peripheral lung tumors is 60 Gy in 3 fractions with a total BED of 180 Gy. In Europe, Japan, and China, however, a BED >100 Gy is more commonly delivered in 4-10 fractions. Particularly in China, regimens with fraction size less than 12 Gy have been preferred. Selection of fractionation should maximize the therapeutic ratio of tumor control versus normal tissue toxicity by taking the tumor size and location into consideration for an optimized therapeutic gain [156] [157]. Overall, for tumors less than 3 cm, there is no significant difference in tumor control rates between various fractionation regimens as long as more than 100 Gy BED is given [150, 158]. For tumors larger than 3 cm, higher doses (BED of 120 Gy or above) may be needed. Similar to RODS, distant failure is the main cause of death [159]. Fractionation regimens with tumor BED around 120 Gy in 3-5 fractions include 16 Gy x 3, 13 Gy x 4, and 11 Gy x 5. The available data are compelling enough for SBRT to be considered an established treatment option in patients who are medically inoperable or for those patients who have refused surgical resection [132, 150, 160].

1.2.2

Toxicity of SBRT

Toxicity following SBRT has been limited. Reported long-term toxicity exceeding grade 2 Common Toxicity Criteria (CTC v. 3.0) is seen in less than 10% of patients and was mainly observed in patients with large or centrally located tumors [121, 135, 161, 162] when doses to the proximal bronchial tree were not strictly limited. In the series by Onishi [129], pulmonary complications exceeding grade 2 were observed in 14 patients (5.4%). Timmerman, et al. reported the need for caution when a BED of 180–210 Gy was administered for centrally located tumors adjacent to the mediastinum [134]. In the patients treated by Lagerwaard, et al., using a 'risk-adapted' approach with the BED limited to 105 Gy for central tumors, early toxicity was mild with fatigue (32%), nausea (10%), and chest pain (8%) as the most frequently encountered acute side effects [135]. Late toxicity was uncommon with radiation pneumonitis exceeding grade 2 in 6 patients (3%). Rib fractures and chronic pain syndromes located at the chest wall were observed in 4 and 3 patients, respectively.

1.2.3

Quality of Life After SBRT

Data on quality of life (QOL) is limited after SBRT for NSCLC. For stage I NSCLC, QOL was assessed in 39 patients treated with SBRT by using The European Organization for Research and Treatment of Cancer Quality of Life Questionnaire (EORTC QLQ) C30 and the QLQ LC13 lung cancer-specific questionnaire. Assessments were done before treatment, at 3 weeks, and at 2, 4, 6, 9, and 12 months after treatment, and until death or progressive disease. Toxicity was evaluated using CTCAE, v. 3.0. Emotional functioning improved significantly after treatment. Other functional scores, QLQ C30, and QLQ LC13 lung symptoms (such as dyspnea and cough) showed no significant changes. [164]. These results may be better than those reported for 3DCRT, RFA, and surgical resection. Using Markov model analysis, a recent cost effectiveness study report indicates that SBRT may offer comparable OS and quality-adjusted life expectancy as compared with surgical resection [266]. Randomized prospective studies comparing surgery vs. SBRT in early-stage lung cancer are warranted to further investigate the relative survival, quality of life, and cost characteristics of both treatment paradigms [266].

In this trial, quality of life endpoints will not be evaluated; however, provided that the primary hypothesis and performance metrics are satisfied, the subsequent phase III trial will incorporate detailed QOL measures in order to definitively and comprehensively evaluate SBRT for larger scale clinical utility.

1.3 Translational Research

1.3.1

Background/Hypothesis

Severe pulmonary complications occur in about 10-20% patients after lobectomy [192-198]. After SBRT, 10% of patients experience grade ≥ 3 radiation-induced lung toxicity (RILT) [199-201]. Currently, there are no well-established methods to predict which patients will experience lung toxicity. In general, the risk of pulmonary toxicity increases with decreasing pulmonary reserve, larger radiation treatment volumes, and the use of concurrent chemotherapy. Many dosimetric factors, such as mean lung dose, V20, and D30 [202-209], have been associated with the risk of lung toxicity after radiation. However, these associations have not enabled prediction of which patients will experience lung toxicity. The mechanisms of RILT are not well understood; however, several reports have suggested a possible role of pro-fibrogenic and pro-

inflammatory cytokines such as Interleukin-1 (IL-1), IL-6, IL-8, IL-10, TNF- α , platelet-derived growth factor and transforming growth factor beta 1 (TGF β 1) [210-218]. Among these factors, TGF β 1 has been the most extensively studied. TGF β 1 stimulates connective tissue formation and decreases collagen degradation resulting in fibrosis. It also plays an important role in the inhibition of epithelial cell proliferation. Researchers from Duke University have reported that the plasma TGF β 1 at the end of radiation correlates with symptomatic lung toxicity in patients treated with definitive radiation therapy [219, 220]. Kong, et al. further demonstrated that the loss of mannose 6-phosphate insulin-like growth factor-2 receptor contributes to increased TGF β 1 levels and subsequent radiation-induced pneumonitis [221]. In patients treated with an escalated dose of radiation, Anscher, et al. found a significant correlation between TGF β 1 levels and late grade ≥ 3 non-pulmonary radiation toxicity [222]. Additional reports have shown that elevated plasma levels of TGF β 1 4 weeks into the course of conventionally fractionated conformal radiation therapy are highly correlated with the occurrence of grade ≥ 2 RILT [210, 223]. A combined analysis of University Michigan and Peking Union of Medical College data further confirmed this finding [224].

Data also has been published demonstrating an association between RILT and levels of IL-1, IL-6, and IL-8 [215, 216, 225-228]. IL-1 (IL-1 α and IL-1 β) is produced by macrophages, monocytes, fibroblasts, and dendritic cells and is an important mediator of the inflammatory response of many tissues [229-232]. IL-1 β promotes inflammation in injured lung tissue, and has been reported to be significantly associated with RILT [216, 233]. IL-6 also is a major mediator of the acute-phase inflammatory response and is synthesized by a variety of cells in the lung parenchyma. Researchers have demonstrated a trend toward increased plasma concentrations of IL-6 after thoracic RT [212, 216]. Animal models also have confirmed these trends [228, 237, 238]. In addition, IL-8, a member of the CXC chemokine family, is believed to serve as a chemical signal that attracts neutrophils to the site of inflammation [239-241]. Significant differences in the median values of IL-8 were observed between patients with and without symptomatic RILT [225]. Overall, plasma IL1, IL-6, and IL-8 levels may serve as a predictor for RILT after conventionally fractionated radiation therapy [212, 216]. Most recently, it was reported that the plasma level of IL-8 prior to and during conventionally fractionated radiation therapy is significantly associated with grade ≥ 2 RILT [242].

Genomic markers also have shown promise in helping to elucidate the mechanism of RILT. The single nucleotide polymorphisms (SNP) of several specific genes found in white blood cells have been shown to be elevated in the setting of radiation-induced injury in several organs [243-245]. CT/CC genotypes of TGF β 1 rs1982073:T869C genes are associated with a lower risk of RILT in patients with NSCLC treated with definitive chemoradiation [246]. It also recently was demonstrated that the frequency of the 7351C allele of Tissue Plasminogen Activator, which is associated with TGF β 1 activation is increased in patients with grade ≥ 2 RILT when compared to historical controls (0.73 vs. 0.68, $p = 0.01$)[247].

Protein elevations also may hold cues as to the mechanism of RILT. It has been demonstrated that there are differential changes in protein-associated pathways between animals sensitive to and resistant to radiation lung damage [248]. Using a multiplexed quantitative proteomics approach involving ExacTag labeling, RP-HPLC, and LC-ESI-MS/MS, over 100 proteins have been identified and quantified in platelet-poor plasma. C4b-binding protein alpha chain, complement C3, and vitronectin have significantly higher expression levels in patients with grade ≥ 2 RILT. Interestingly, all of these proteins are associated with inflammatory pathways that interact with IL-1 β , TNF, and TGF- β 1 [249].

Given these previous studies, we hypothesize that blood-based biomarkers, including plasma TGF β 1, will be able to predict which patients will develop grade ≥ 3 pulmonary complications after treatment with either SBRT or surgery, and specimens will be banked for future translational research. Translational research endpoints will not be evaluated in this trial. If the primary hypothesis and performance metrics are satisfied, the subsequent phase III trial will incorporate translational research endpoints.

1.4 Study Rationale/Hypothesis

Standard therapy for stage I NSCLC has been R0 resection, consisting primarily of lobectomy with lymph node dissection/sampling (RODS), generating 3-5 year OS rates of 50-80%, local control rates of 70-90%, grade 3 complication rates of 10-30%, and hospital stays of 1-3 weeks. A significant number of patients are either medically inoperable or refuse surgical intervention. Historically, conventional fractionated 2DRT or 3DCRT (60-70 Gy over 5-7 weeks) has been reserved for medically inoperable patients with a 5-year cause-specific survival rate of ~30%, local control rate of 15-50%, grade 3 toxicity rate of 5%, radiation therapy cost of \$20,000 to \$30,000, and outpatient treatment duration of 6-7 weeks. With advancement of radiation technology, SBRT has become available at most of the large centers and generates local tumor control rates of 85% to 95% in both medically inoperable and operable patients [127] with relative rare adverse events, such as pneumonitis and rib fracture. The role of SBRT in patients who are operable candidates is being evaluated in a phase II clinical trial, RTOG 0618, which was initiated in 2008 and completed accrual as of March 1, 2010.

The central hypothesis of this study is that SBRT, although potentially yielding a lower local-regional tumor control rate will provide equivalent OS and significantly better QOL than RODS in patients with stage I NSCLC. The study population includes medically operable patients with PET/CT staged T1N0 (Stage IA) NSCLC. Eligible patients will be randomized to 2 arms. Patients enrolled to Arm 1 will be treated with surgical resection. Patients enrolled to Arm 2 will be treated with SBRT of 55 Gy in 5 fractions (BED 118 Gy) for both peripheral and central tumors. We selected this fractionation as it is also a safe regimen [280, 281]. Three-year OS, 3-year local progression-free survival, disease-specific survival, treatment cost, duration of hospital stay, and time to local progression will be compared between the 2 arms. By completing this trial, we hope to be able to provide necessary preliminary information to continue to a definitive trial to determine whether high-dose SBRT will generate outcomes comparable to those of surgical resection in patients with stage I NSCLC.

1.5 Study Significance

The outcome of this study will be clinically significant for several reasons: If SBRT is proven to be at least equivalent to RODS, patients with stage I NSCLC (approximately 20,000 new cases annually worldwide) would have a non-invasive treatment option that may offer significant advantages. With respect to advancing the SBRT approach:

1. This trial will provide important data regarding potential differences in local-regional tumor control and patterns of failure between SBRT and RODS. These endpoints are critical to establishing equivalence of the 2 approaches with respect to survival.
2. A key secondary objective of this trial is to qualitatively and quantitatively assess the logistical feasibility of joint clinical trial conduct between the RTOG and institutions in China. Parameters measuring feasibility include pre-registration requirements, patient accrual rate, eligibility rate, randomization conduct, baseline forms completion, follow-up forms completion/delinquency, and loss to follow-up rate. This study will serve to motivate the building and evaluation of logistics for international collaboration in the cooperative group setting, and serve to develop a critical means of expanding participation and conducting trials more rapidly, as well as delivering an advantageous therapy to populations of great need.
3. The banking of biological specimens will provide for future identification of molecular prognostic factors for response to these very different therapeutic modalities.

2.0 OBJECTIVES

2.1 Primary Objective

2.1.1 The primary aim of this study is to determine whether SBRT provides local-regional tumor control that is not more than 15% lower than RODS. This difference is considered a threshold deficit at which overall survival (OS) will not be compromised.

2.2 Secondary Objectives

2.2.1 To qualitatively and quantitatively assess feasibility of this joint RTOG-China clinical trial. Parameters to be assessed include satisfaction of pre-registration requirements (e.g. surgical and RTQA credentialing), patient accrual rate, patient eligibility rate, randomization conduct baseline forms completion and timeliness, follow-up forms completion/delinquency, and loss to follow-up rate;

2.2.2 To compare overall survival and disease-free survival between study arms;

2.2.3 To estimate and compare time to local-regional failure, time to distant metastases, and patterns of failure between study arms;

2.2.4 To compare treatment toxicities using the Common Terminology Criteria for Adverse Events (CTCAE, v. 4) between study arms; specific comparisons will include adverse events at 1, 3, 12, 24, and 36 months post-therapy;

3.0 PATIENT SELECTION

3.1 Conditions for Patient Eligibility (10/22/14)

3.1.1 Stage I NSCLC (AJCC, 7th ed.), T1N0M0; **note:** T1N0 disease must be confirmed by FDG-PET/CT (see Section 3.1.5).

Biopsy confirmation of diagnosis is strongly recommended but not required. If the biopsy is attempted and non-diagnostic, if the patient refuses biopsy, or if the risk of biopsy is considered too high, patients may be enrolled if the mass is suspicious for NSCLC based on 2 or more of the following criteria:

- Positive smoking history;
- Absence of benign calcifications within suspicious nodule;
- Activity on PET greater than normal tissue;
- Evidence of growth compared to previous imaging;
- Presence of spiculation.

The following primary cancer types are eligible: squamous cell carcinoma; adenocarcinoma; large cell carcinoma/ large cell neuroendocrine carcinoma; non-small cell carcinoma not otherwise specified.

3.1.2 Patients with hilar or mediastinal lymph nodes ≤ 1 cm and no abnormal hilar or mediastinal uptake on PET and CT will be considered N0. Mediastinal lymph node biopsy is required for patients with visible nodes: patients with > 1 cm hilar or mediastinal lymph nodes on CT or with nodes appearing as abnormal on PET (including suspicious but nondiagnostic uptake). Such patients will not be eligible unless directed biopsies of all abnormal lymph nodes are negative for cancer or these nodes demonstrate a lack of change during the prior 6 months and thus are considered to be non-malignant.

3.1.3 The patient must be considered a reasonable candidate for surgical resection using a lobectomy or pneumonectomy of the primary tumor within 6 weeks prior to registration, according to the following criteria based on the American College of Chest Physicians guidelines [165]:

- A qualified thoracic surgeon should make the determination that there would be a high likelihood of negative surgical margins;
- Baseline FEV1 $>60\%$ predicted, postoperative predicted FEV1 $>40\%$ predicted;
- Diffusion capacity of the lung for carbon monoxide (DLCO) $>60\%$ predicted, postoperative predicted DLCO $> 40\%$ predicted;
- No baseline hypoxemia and/or hypercapnia;
- If the estimated postoperative FEV1 or DLCO $<40\%$ predicted indicates an increased risk for perioperative complications, including death, from a standard lung cancer resection (lobectomy or greater removal of lung tissue), then cardiopulmonary exercise testing to measure maximal oxygen consumption (VO₂max) must be $>60\%$;
- No severe pulmonary hypertension;
- No severe cerebral, acute or chronic cardiac, or peripheral vascular disease;

3.1.4 Pleural effusion, if present, must be deemed too small to tap under CT guidance and must not be evident on chest x-ray. Pleural effusion that appears on chest x-ray will be permitted only if there is no evidence of malignancy after invasive cytologic assessment.

3.1.5 Appropriate stage for protocol entry, including no distant metastases, based upon the following minimum diagnostic workup:

- History/physical examination, including documentation of weight within 6 weeks prior to registration;
- Evaluation by an experienced thoracic surgeon within 6 weeks prior to registration;
- FDG-PET/CT scan for staging and RT plan within 4 weeks prior to registration;
- CT scan (preferably with intravenous contrast, unless medically contraindicated) within 4 weeks prior to registration to include the entirety of both lungs, the mediastinum, liver, and adrenal glands; primary tumor dimension will be measured on CT scan.

3.1.6 Zubrod Performance Status 0-1 within 6 weeks prior to registration;

3.1.7 Age ≥ 18 ;

3.1.8 For women of childbearing potential, a serum or urine pregnancy test must be negative within 72 hours prior to registration;

3.1.9 Women of childbearing potential and male participants who are sexually active must practice adequate contraception during treatment if assigned to treatment with SBRT.

3.1.10 Patients must provide study specific informed consent prior to study entry.

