[name], PhD
Shanghai Cancer Center/Fudan University
Shanghai 200032, China
[name]
[contact]

U.S. Radiation Oncology Co-Chairs

[name] and [name], PhD
MD Anderson Cancer Center
Houston, TX 77030
[contact]/[contact]
[contact]

China Medical Physics Co-Chair

[name]
Chinese Academy of Medical Science
Beijing 10021, China
[name]/ [contact]
[contact]

U.S. Medical Oncology Co-Chair

[name]
University of Michigan Cancer Center
Ann Arbor, MI 48109, USA
[contact]/[contact]
[contact]

China Medical Physics Co-Chair

[name]
Shandong Cancer Hospital and Institute
Jinan, Shandong 250117, China
[name]/[contact]
[contact]

U.S. Senior Statistician

[name]
Radiation Therapy Oncology Group/ACR
and University of Chicago
[name]
Philadelphia, PA 19103
[contact]/[contact]
[contact]

China Medical Oncology Co-Chairs

[name] and [name]
Shanghai Lung Cancer Center/Jiaotong University
Shanghai 200030, China
[name]
[contact]

China Medical Oncology/Pulmonary Co-Chair

[name], PhD
Zhongshan Hospital/Fudan University
Shanghai, China
[name]
[contact]

TABLE OF CONTENTS

Schema

Eligibility Checklist

- 1.0 Introduction
- 2.0 Objectives
- 3.0 Patient Selection
- 4.0 Pretreatment Evaluations/Management
- 5.0 Registration Procedures
- 6.0 Radiation Therapy
- 7.0 Drug Therapy
- 8.0 Surgery
- 9.0 Other Therapy
- 10.0 Tissue/Specimen Submission
- 11.0 Patient Assessments
- 12.0 Data Collection
- 13.0 Statistical Considerations

References

- Appendix I - Sample Consent Form
- Appendix II - Study Parameters
- Appendix III - Performance Status Scoring
- Appendix IV - Staging System
- Appendix V - Thoracic Surgeon Credentialing Form
- Appendix VI - Nodal Atlas

RTOG FOUNDATION STUDY 3502

**POSTILV: A Randomized Phase II Trial in Patients with Operable Stage I Non-Small Cell Lung Cancer:
Radical Resection versus Ablative Stereotactic Radiotherapy**

SCHEMA

	R		R		Follow up for Arms 1 and 2
	E		A	Arm 1: R0 resection with nodal dissection/sampling	
Patients with pathologically proven, medically operable CT-staged T1N0 NSCLC	G	FDG-PET/CT staging	N D	(RODS)	
	S	to confirm	O		If recurrence then salvage treatment:
	T	T1N0 disease*	M	Arm 2: SBRT given every other day	surgery, radiation, or systemic therapy
	E		I	11 Gy in 5 fractions to a total dose	
	R		Z	of 55 Gy in 10-15 days with an	
			E	inter-fraction interval of 2-3 days	

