*Patients with T > 3 cm or N+ disease will be treated off study per standard of care and will not be followed.

Note: All participating institutions must be credentialed for participating surgeons, a dry-run case, phantom irradiation, IGRT, and 3DCRT (or IMRT, if used) prior to registering patients to the study; see Section 5.1.

Patient Population: (See Section 3.0 for Eligibility)

Patients must have histologically proven CT and PET/CT confirmed Stage I, T1N0M0 non-small cell lung cancer (NSCLC); patients must be medically operable

Required Sample Size: 76

Institution #

3502

Case #

ELIGIBILITY CHECKLIST – STEP 1 (10/22/14)
(page 1 of 4)

PRE-REGISTRATION CREDENTIALING for participating surgeons, a dry-run case, phantom irradiation, IGRT, AND 3DCRT (or IMRT, if used) IS REQUIRED.

(Y) 1. Was stage I non-small cell lung cancer (NSCLC) confirmed by biopsy (strongly recommended) or is the mass suspicious for NSCLC based on 2 or more criteria listed in Section 3.1.1?

(Y) Is the cancer one of the types eligible for the study as specified in Section 3.1.1?

(N) Any histologic evidence of pure bronchioloalveolar cell carcinoma subtype?

(N) 2. Is the primary tumor > 3 cm?

(Y) 3. Is patient nodal status N0 per definition in Section 3.1.2. ?

(Y/N) Are there hilar or mediastinal lymph nodes > 1 cm on computed tomography (CT) or any size lymph nodes demonstrating suspicious uptake on positron emission tomography (PET) scan?

(Y) If yes, are all lymph nodes > 1 cm on CT or demonstrating suspicious uptake on PET scan negative for NSCLC on biopsy?

(N) 4. Does the patient have metastatic disease (M1)?

(Y) 5. Is the primary tumor predicted to be technically resectable with high likelihood of negative surgical margins by a thoracic surgeon?

(Y) 6. Is the patient medically operable as defined in Section 3.1.3?

(Y) 7. Do the patient's PFTs meet the criteria specified in Section 3.1.3?

(Y/N) 8. Is pleural effusion present?

(Y) If yes, is the effusion too small to tap under CT guidance and not evident on chest x-ray? (Pleural effusion that appears on chest x-ray and only after thoracotomy or other invasive thoracic procedure will be permitted.)

(Y) 9. Is the patient's Zubrod Performance Score 0-1?

(Y) 10. Is patient ≥ 18 years of age?

(Y/NA) 11. If a female of childbearing potential or an sexually active male, has the patient agreed to use an effective method of contraception?

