3.2 Conditions for Patient Ineligibility

3.2.1 Direct evidence of regional or distant metastases after PET and surgical staging studies, or synchronous primary malignancy or prior invasive malignancy in the past 3 years, with the following exceptions:

- carcinoma in situ;
- early stage skin cancer that has been definitively treated;
- when an invasive malignancy has been treated definitively and the patient has remained disease free for ≥ 3 years;

3.2.2 Primary tumors >3 cm;

3.2.3 Prior systemic chemotherapy or thoracic surgery involving lobectomy or pneumonectomy;

3.2.4 Prior radiotherapy to the region of the study cancer that would result in overlap of radiation therapy fields;

3.2.5 Pure bronchioloalveolar carcinoma subtype of non-small cell lung cancer;

3.2.6 Active systemic, pulmonary, or pleural pericardial infection;

3.2.7 Pregnancy or women of childbearing potential and men who are sexually active and not willing/able to use medically acceptable forms of contraception; this exclusion is necessary because the treatment involved in this study may be significantly teratogenic.

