11.1.1 Details of Follow-Up Evaluations

11.1.1.1 In follow up, PET and CT scans are required to document disease relapse/progression. Biopsy of the relapse/progression site is encouraged, but not required. Submission of the biopsy report (if applicable) and scan reports is required (see Schedule of Forms). Submission of imaging studies (scans with recurrent disease and the scans used for reference) is required for patients with recurrent disease.

Chest CT with IV contrast will be performed at least at 3, 6, 9, 12, 18, 24, and 36 months after completion of treatment (the date of surgery or at the last day of SBRT) per current standard of care. Response evaluation after SBRT can sometimes be difficult as fibrosis and subclinical radiographic changes are observed in a majority of patients. A solid pattern of fibrosis often may be misinterpreted as recurrent disease [267]. Regular radiological follow-up is required to establish local control. 18F-FDG PET can be helpful in distinguishing fibrosis from tumor recurrence, but treated volumes can show 18F-FDG uptake related to therapy for at least 12 months after treatment [162]. Careful radiological follow-up of patients is paramount in patients treated by RODS, as salvage surgery or definitive chemoradiotherapy might still be possible in case of local or regional recurrence [268-269].

11.1.1.2 In follow up, pulmonary function tests should be done per the treating physician's discretion.

11.1.1.3 After treatment is completed, patients will be seen in follow up every 3 months for years 1-2 years, every 6 months for year 3, then annually until publication of study results.

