12.1 Summary of Data Submission (6-AUG-2018)

Item	Due
Initial Evaluation Form (I1) Pathology Report (P1)	Within 2 weeks of registration
Radiotherapy Form (T1)	Within 1 week of RT end
Surgical Form (S1) Surgical Procedure Report (S2) Surgical Pathology Report (S5) NOTE: The S2 and S5 should be de-identified and emailed to [contact] as PDF files	Within 4 weeks after protocol surgery
Follow-up Form (F1)	Every 3 months for years 1-2 years, every 6 months for year 3, then annually until publication of study results

12.2 Summary of Dosimetry Digital Data Submission (Submit to RTOG Headquarters; see Section 12.2.1) (6-AUG-2018)

Item	Due
Preliminary Dosimetry Information (DD) Digital Data Submission – Treatment Plan submitted in DICOM format to RTOG via TRIAD, exported from treatment planning machine by Physicist Digital data submission includes the following: 
• Planning CT• RT Structure File including all required tumor volumes and critical normal structures• RT Plan File for final plan• RT Composite Dose File for treated beams• Digital DVH data including all required tumor volume and critical normal structures• Digital Data Submission Form (DDSI) [on the RTOG website, Foundation study 3502, under Forms]	Within 1 week of start of RT

Final Dosimetry Information Radiotherapy Form (T1) Daily Treatment Record (T5) [Copy of daily treatment chart submitted via email to [contact].]	Within 1 week of end of RT
PET and/or CT progression scans (MR) PET and/or CT progression reports (ME) Digital Data Submission Form (DDSI) [on the RTOG web site, Foundation study 3502, under Forms]	At time of progression
NOTE: For all digital data submissions (preliminary, final Dosimetry or PET/CT scans for progression), sites must complete a Digital Data Submission Form (DDSI) via the RTOG web site. Also, sites will notify RTOG via e-mail [contact] after any digital data is submitted. The e-mail must include study number, site name, and case numbers.	
Modified digital patient data as required by RTOG will be submitted via TRIAD.	

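### Does entry without a tissue diagnosis, with a resection specimen in one arm only, bias the primary comparison?

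*Combined protocol and SAP*

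**What the plan says.** Section 3.1.1 states "Biopsy confirmation of diagnosis is strongly recommended but not required". It opens a second route "If the biopsy is attempted and non-diagnostic, if the patient refuses biopsy, or if the risk of biopsy is considered too high": at least two of five features (smoking history, no benign calcification, PET activity, growth, spiculation). Item 1 of the eligibility checklist asks for biopsy confirmation "or is the mass suspicious for NSCLC based on 2 or more criteria listed in Section 3.1.1". Both carry the date 10/22/14. The schema still reads "Patients with pathologically proven, medically operable CT-staged T1N0 NSCLC", and the patient-population statement below it likewise requires histological proof.

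Section 3.1.1 lists the eligible cancer types, and Section 3.2.5 excludes "Pure bronchioloalveolar carcinoma subtype of non-small cell lung cancer". Section 12.1 collects a baseline pathology report (P1) and, after protocol surgery, a surgical pathology report (S5). SBRT has no counterpart to S5.

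Section 13.3 raises the sample size from 72 to 76 for ineligibility and attrition together. Section 13.5.4 sets a 95% benchmark for eligibility upheld at central review. Section 13.5.1 compares the two arms with a test of proportions and does not say which patients enter it.

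**The concern.** For a patient randomised without tissue, histology can emerge from treatment in RODS but not in SBRT. A resection may show a benign nodule, a tumour that is not NSCLC, or an excluded subtype. If such patients were declared ineligible and removed, the removal would rest on information from one arm and the randomised comparison would be broken. Benign lesions would rarely recur, so taking them out of RODS lowers the apparent surgical control rate and flatters SBRT. Removing aggressive ineligible cancers from RODS does the reverse.

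Even with nobody removed, benign lesions in both arms pull the difference towards zero, which in a non-inferiority trial favours the claim. With 36 per arm and a 15-point margin, a shift of one or two points deserves a check. The contradictory wording on proof of diagnosis adds to the impression that the entry rule was not thought through.

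**Working it through.** **The plan's own figure.** Inputs from Section 13.3: control of 90% (RODS) and 75% (SBRT), power 0.80, 36 per arm. With a pooled rate of 0.825, a one-sided 0.20 test of a difference gives

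n = [0.8416√(2 × 0.825 × 0.175) + 0.8416√(0.90 × 0.10 + 0.75 × 0.25)]² / 0.15² = 35.7, so 36.

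A non-inferiority calculation with 90% in both arms and one-sided 0.10 gives 0.18 × (1.2816 + 0.8416)² / 0.15² = 36.06, so 37. Both are close to the stated size. The significance level is not clearly stated, so 0.10 is assumed below. Inflation: 72 / 0.95 = 75.8, so 76.

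**Is removal on the specimen planned?** Setting the sections side by side:

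- Sections 3.1.1 and checklist item 1: an unbiopsied patient is eligible if the mass looks suspicious on two features. That is settled before registration, and a later benign report does not make it untrue.
- Sections 8.1.5 and 9.1.1: care is described for patients whose resection shows nodal or T2 disease. They are not declared off study.
- Section 11.3: follow-up and data collection continue if protocol treatment stops.
- Section 13.4: reporting waits until all patients have two years of follow-up or a primary event.
- Section 13.5.4: the 95% figure is a descriptive feasibility benchmark, not an analysis rule.
- Section 5.4.1: patients found not to have T1N0 disease on PET/CT leave before randomisation, so the arms are unaffected.

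None of these defines the analysis set, but none removes a patient on resection pathology.

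**How large could the effect be?** Let b be the benign share of all randomised patients and f the fraction of benign SBRT lesions misread as progression. The documents give neither. I take b = 2%, 5% and 10% (for example 20% unbiopsied × 10% benign, 20% × 25%, 40% × 25%). True control among cancers is set on the margin, 90% against 75%.

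- SBRT control = 0.75(1 − b) + b(1 − f)
- RODS control = 1 − 0.10(1 − b) if all are kept; 0.90 if benign cases are removed
- Apparent deficit = 0.15 − 0.15b + bf (kept); 0.15 − 0.25b + bf (removed)

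The chance of declaring non-inferiority comes from exact binomial enumeration of an unpooled Wald test. In the removed case the RODS sample size is itself binomial (36, 1 − b). With f = 0:

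| b | Deficit, kept | False claim, kept | Deficit, removed | False claim, removed |
|---|---|---|---|---|
| 0 | 15.0 | 10.3% | 15.0 | 10.3% |
| 2% | 14.7 | 10.9% | 14.5 | 11.9% |
| 5% | 14.25 | 12.0% | 13.75 | 13.8% |
| 10% | 13.5 | 13.9% | 12.5 | 17.1% |

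For scale, with no benign lesions at all, 35 or 37 per arm gives 11.1% under the same test. The 2% kept row is therefore within the discreteness of the binomial.

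**The sign is not fixed.** Section 11.1.1.1 warns that "A solid pattern of fibrosis often may be misinterpreted as recurrent disease". From the formulas, the deficit returns to 15 points at f = 0.15 (kept) or f = 0.25 (removed) and exceeds it beyond that. At f = 0.10 the kept figures are 10.5%, 10.8% and 11.4%. If instead 5% are aggressive ineligible cancers with 50% control (assumed), removed from RODS only, SBRT control is 0.95 × 0.75 + 0.05 × 0.50 = 73.75%. The deficit is then 16.25 points and the false-claim rate about 8.4%.

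**What would a tissue-proven analysis show?** The 90% interval half-width is 1.645√[(0.09 + 0.1875)/n]: 14.4 points at n = 36 and 16.1 points at n = 29 (20% unbiopsied, assumed). The dilution it would have to detect is 0.15b, or 0.3 to 1.5 points.

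**The case for a change.** The best argument for a change is that it would be nearly free. One sentence could fix the analysis set as all randomised patients and confine eligibility review to information available before randomisation. A small non-inferiority trial should settle this before the data are seen, and a bias of unknown sign is a reason to have the rule. Inflating the sample size for ineligible patients hints that some might not be counted. The sections that suggest retention deal with upstaging, timing and data collection, not with benign or excluded histology.

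Part of this stands. The analysis set is unwritten, and the list of eligible cancer types together with Section 3.2.5 leaves some room to call a resected patient ineligible. Anyone reading the results should check that the denominators match the numbers randomised. What does not stand is the step from an unwritten policy to an expected bias. The missing analysis set would be just as missing if biopsy were mandatory. The dilution that remains when everyone is kept follows from a deliberate entry rule that applies equally to both arms, and writing the rule down would not remove it. The tissue-proven subset has a half-width wider than the 15-point margin and could not measure an effect of 1.5 points or less.

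**Conclusion.** The concern does not call for a change. The unnamed analysis population is a gap that analysts fill in the ordinary way, by analysing randomised patients in their assigned arm. The entry criteria support that reading, because an unbiopsied patient meets them on features recorded before randomisation. The schema's requirement for proof of diagnosis conflicts with Section 3.1.1. The dated criteria and the matching checklist item govern who is enrolled, so the schema wording is a clerical leftover with no effect on the analysis.

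If all patients are kept, the false non-inferiority rate moves from 10.3% to between 10.9% and 13.9% for benign shares of 2% to 10%. The larger figures, up to 17.1%, need both the highest assumed share and a one-arm removal that the plan nowhere states. All of these rest on assumed benign shares, an assumed one-sided level of 0.10, and benign lesions never being scored as failures; relaxing the last can cancel or reverse the shift. P1 and S5 reports are already collected, so the number entered without tissue and the surgical findings can be described without any amendment.
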